³Within each question, response choices will be ordered by percent endorsing, descending, ties will go in order presented to respondents. For items with more than 5 response options, the top 5 selected response options within each item at baseline will be bolded in tables for subsequent timepoints.

^{*&}quot;Other" responses and open-ended text responses will be presented in an appendix.

Table 1.3.2. PLWHIV Views on IC Administration Model, Month 3 (N=XX)

Question	Number of Participants at Month 3	Response	n (%)
		Very acceptable	n (%)
		Somewhat acceptable	n (%)
		A little acceptable	n (%)
1. How acceptable is it to		Neutral	n (%)
you to come to the infusion center for CABENUVA? ¹	XX	A little unacceptable	n (%)
		Somewhat unacceptable	n (%)
		Very unacceptable	n (%)
		Missing	n (%)
		Convenient location of the infusion center	n (%)
	XX	Ease of parking at the infusion center	n (%)
		Convenient hours for the infusion center	n (%)
		Ease of scheduling and rescheduling appointments at the infusion center	n (%)
2. William and the collection of the collection o		More privacy at the infusion center	n (%)
2. What are the advantages of going to the infusion center to receive		I like that people do not know what medication I am there to receive	n (%)
CABENUVA? ^{2,3}		Reduced stigma at the infusion center	n (%)
		Injections are not available at my provider's office	n (%)
		No advantages of receiving CABENUVA at the infusion center	n (%)
		Other*	n (%)
		Missing	n (%)
		Inconvenient location of the infusion center	n (%)
3. What are the		Difficulty of parking at the infusion center	n (%)
disadvantages of going to the infusion center to receive CABENUVA? ^{2,3}	XX	Unfamiliar with routine at the infusion center	n (%)
		Unfamiliar with the infusion center staff	n (%)
		Inconvenient hours for the infusion center	n (%)

Question	Number of Participants at Month 3	Response	n (%)
		Less privacy at the infusion center	n (%)
		More stigma at the infusion center	n (%)
		Decreased contact with my HIV provider	n (%)
		Difficulty scheduling and rescheduling appointments at the infusion center	n (%)
		Too many appointments between the infusion center and my HIV providers	n (%)
		Too many lab draws	n (%)
		Infusion center doesn't know how to manage the pain or side effects of CABENUVA	n (%)
		I don't want other people at the infusion center to know I have HIV	n (%)
		No disadvantages of receiving CABENUVA at the infusion center	n (%)
		Other*	n (%)
		Missing	n (%)
	XX	Very convenient	n (%)
		Somewhat convenient	n (%)
		A little convenient	n (%)
4. How convenient is it for you to get to the infusion		Neutral	n (%)
center for your CABENUVA visits? ¹		A little inconvenient	n (%)
		Somewhat inconvenient	n (%)
		Very inconvenient	n (%)
		Missing	n (%)
		1-15 minutes	n (%)
		16-30 minutes	n (%)
5. How long does it typically take you to get to the	XX	31-45 minutes	n (%)
infusion center? ¹	^^	46-60 minutes	n (%)
		More than 60 minutes	n (%)
		Missing	n (%)

Question	Number of Participants at Month 3	Response	n (%)
		Very acceptable	n (%)
		Somewhat acceptable	n (%)
		A little acceptable	n (%)
6. How acceptable is the	VV	Neutral	n (%)
time it typically takes you to get to the infusion center? ¹	XX	A little unacceptable	n (%)
		Somewhat unacceptable	n (%)
		Very unacceptable	n (%)
		Missing	n (%)
		1-15 minutes	n (%)
7 N		16-30 minutes	n (%)
7. Not including your first visit, how much time have	V0/	31-45 minutes	n (%)
you been spending at the infusion center for your CABENUVA visits? ¹	XX	46-60 minutes	n (%)
CABENOVA VISILS?*		More than 60 minutes	n (%)
		Missing	n (%)
		Very acceptable	n (%)
		Somewhat acceptable	n (%)
		A little acceptable	n (%)
8. How acceptable is the amount of time you spend	VV	Neutral	n (%)
at the infusion center for your CABENUVA visits? ¹	XX	A little unacceptable	n (%)
		Somewhat unacceptable	n (%)
		Very unacceptable	n (%)
		Missing	n (%)
		Extremely easy	n (%)
9. How easy or difficult was it to schedule your monthly	XX	Very easy	n (%)
injection visits at the infusion center?1	^^	Somewhat easy	n (%)
		Neutral	n (%)

Question	Number of Participants at Month 3	Response	n (%)
		Somewhat difficult	n (%)
		Very difficult	n (%)
		Extremely difficult	n (%)
		Missing	n (%)
		Extremely easy	n (%)
		Very easy	n (%)
		Somewhat easy	n (%)
10. How easy or difficult		Neutral	n (%)
was it to reschedule your injection visits at the	XX	Somewhat difficult	n (%)
infusion center, if needed?1		Very difficult	n (%)
		Extremely difficult	n (%)
		I have not had to reschedule any visits yet	n (%)
		Missing	n (%)
		Extremely satisfied	n (%)
		Very satisfied	n (%)
		Somewhat satisfied	n (%)
11. How satisfied are you with the appointment	VV	Neutral	n (%)
reminders you receive from the infusion center?1	XX	Somewhat dissatisfied	n (%)
		Very dissatisfied	n (%)
		Extremely dissatisfied	n (%)
		Missing	n (%)
		Extremely satisfied	n (%)
12. How satisfied are you with the convenience of the		Very satisfied	n (%)
infusion center hours	XX	Somewhat satisfied	n (%)
available for your injection appointments?1		Neutral	n (%)
		Somewhat dissatisfied	n (%)

Question	Number of Participants at Month 3	Response	n (%)
		Very dissatisfied	n (%)
		Extremely dissatisfied	n (%)
		Missing	n (%)
		Standard business hours during weekdays (e.g., 8am – 5pm)	n (%)
		Early morning during weekdays (e.g., before 8am)	n (%)
13. Which appointment times would be most helpful		Evenings during weekdays (e.g., after 5pm)	n (%)
to you for getting the CABENUVA treatment at the	XX	Weekend mornings	n (%)
infusion center? ^{2,3}		Weekend afternoons	n (%)
		Weekend evenings	n (%)
		Missing	n (%)
	XX	Staff at the infusion center	n (%)
14. If you had questions		My regular HIV provider	n (%)
about CABENUVA treatment in-between appointments		Other staff at my regular HIV provider's office	n (%)
(other than appointment scheduling),		Other people with HIV	n (%)
who did you reach out to for answers to your		Social media	n (%)
question(s)? ^{2,3}		No questions to date	n (%)
		Missing	n (%)
		Extremely satisfied	n (%)
		Very satisfied	n (%)
14a. If "staff at the infusion		Somewhat satisfied	n (%)
center" selected, how satisfied were you with the	VV	Neutral	n (%)
infusion center staff's ability to answer your	XX	Somewhat dissatisfied	n (%)
question(s)? ¹		Very dissatisfied	n (%)
		Extremely dissatisfied	n (%)
		Missing	n (%)

Question	Number of Participants at Month 3	Response	n (%)
		Very acceptable	n (%)
		Somewhat acceptable	n (%)
		A little acceptable	n (%)
15. How acceptable is it for	VV	Neutral	n (%)
you to get labs drawn at the infusion center?1	XX	A little unacceptable	n (%)
		Somewhat unacceptable	n (%)
		Very unacceptable	n (%)
		Missing	n (%)
		Very acceptable	n (%)
	xx	Somewhat acceptable	n (%)
16. How acceptable is it to		A little acceptable	n (%)
go to two separate places for your care (that is, the		Neutral	n (%)
infusion center for CABENUVA and to your		A little unacceptable	n (%)
clinic for your regular HIV appointments)?¹		Somewhat unacceptable	n (%)
		Very unacceptable	n (%)
		Missing	n (%)
17. We know that people can be treated differently		Yes	n (%)
due to factors including, but not limited to, HIV status,		No (skip to question #30)	n (%)
gender, and race. Have you been treated differently, or	XX	Prefer not to answer	n (%)
experienced stigma or discrimination at the infusion center? ¹		Missing	n (%)
		A lot worse	n (%)
17a If year how has your		Somewhat worse	n (%)
17a. If yes, how has your experience at the infusion center compared to your	XX	A little worse	n (%)
experience at your HIV provider's office/clinic?1	^^	About the same	n (%)
provider's office/cliffic?		A little better	n (%)
		Somewhat better	n (%)

Question	Number of Participants at Month 3	Response	n (%)
		A lot better	n (%)
		Missing	n (%)
		Age	n (%)
		Race/ethnicity	n (%)
		Sex	n (%)
		Gender identity	n (%)
		Sexual preference	n (%)
		HIV status	n (%)
18. Do you believe you have been treated differently		Religion	n (%)
based on any of the following factors: ^{2,3}	XX	Physical appearance	n (%)
Ü		Housing status	n (%)
		Due to pregnancy/being pregnant	n (%)
		Other*	n (%)
		None of the above	n (%)
		Extremely comfortable	n (%)
		Missing	n (%)
		Very comfortable	n (%)
	-	Somewhat comfortable	n (%)
		Neutral	n (%)
19. How comfortable are you with the infusion center		Somewhat uncomfortable	n (%)
managing your CABENUVA injections? ¹	XX	Very uncomfortable	n (%)
,		Extremely uncomfortable	n (%)
		Extremely welcome	n (%)
		Missing	n (%)
20. How welcome do you		Very welcome	n (%)
feel at the infusion center? ¹	XX	Somewhat welcome	n (%)

Question	Number of Participants at Month 3	Response	n (%)
		Neutral	n (%)
		Somewhat unwelcome	n (%)
		Very unwelcome	n (%)
		Extremely unwelcome	n (%)
		Extremely respectful	n (%)
		Missing	n (%)
		Very respectful	n (%)
		Somewhat respectful	n (%)
21. How respectful are the		Neutral	n (%)
infusion center staff when you are there for your	XX	Somewhat disrespectful	n (%)
injections? ¹		Very disrespectful	n (%)
		Extremely disrespectful	n (%)
		Missing	n (%)
		Extremely satisfied	n (%)
		Very satisfied	n (%)
		Somewhat satisfied	n (%)
22. How satisfied are you with the level of privacy at	V0/	Neutral	n (%)
the infusion center for receiving your injections? ¹	XX	Somewhat dissatisfied	n (%)
G ,		Very dissatisfied	n (%)
		Extremely dissatisfied	n (%)
		Missing	n (%)
		Very concerned	n (%)
23. How concerned are you		Moderately concerned	n (%)
about unwanted disclosure of your HIV status when	XX	Somewhat concerned	n (%)
attending appointments at your HIV provider's office? ¹		A little concerned	n (%)
		Not at all concerned	n (%)

Question	Number of Participants at Month 3	Response	n (%)
		Missing	n (%)
		Very concerned	n (%)
		Moderately concerned	n (%)
24. How concerned are you		Somewhat concerned	n (%)
about unwanted disclosure of your HIV status when	XX	A little concerned	n (%)
attending appointments at the infusion center ? ¹		Not at all concerned	n (%)
		Extremely satisfied	n (%)
		Missing	n (%)
		Very satisfied	n (%)
		Somewhat satisfied	n (%)
25. How satisfied are you		Neutral	n (%)
with the level of care you are receiving at the infusion	XX	Somewhat dissatisfied	n (%)
center?¹		Very dissatisfied	n (%)
		Extremely dissatisfied	n (%)
		Missing	n (%)
		Extremely positive	n (%)
		Somewhat positive	n (%)
		A little positive	n (%)
26. What is your overall opinion about going to an	VV	Neutral	n (%)
infusion center to receive CABENUVA?¹	XX	A little negative	n (%)
		Somewhat negative	n (%)
		Very negative	n (%)
		Missing	n (%)
27. How does your total		Significantly more cost now	n (%)
monthly out of pocket cost for CABENUVA (how much you have to pay) compare	XX	Somewhat more cost now	n (%)
with how much you paid		About the same cost now	n (%)

Question	Number of Participants at Month 3	Response	n (%)
monthly for your previous oral HIV medication? ¹		A little less cost now	n (%)
If you are receiving CABENUVA injections every		A lot less cost now	n (%)
2 months: Divide your out of pocket cost for		Don't know/Unsure/Not applicable	n (%)
CABENUVA in half to obtain your monthly out of pocket cost for comparison to your monthly cost for oral HIV medication.		Missing	n (%)
		Extremely satisfied	n (%)
		Very satisfied	n (%)
20.11		Somewhat satisfied	n (%)
28. How satisfied are you with how much you are	VV	Neutral	n (%)
paying (out of pocket cost) for your CABENUVA	XX	Somewhat dissatisfied	n (%)
injections? ¹		Very dissatisfied	n (%)
		Extremely dissatisfied	n (%)
		Missing	n (%)

¹ Select one response

Abbreviations: HIV = human immunodeficiency virus; PLWHIV = participants living with human immunodeficiency virus

NOTE: Missing = the number of participants who are eligible to complete a survey at the respective timepoint but did not complete respective item; Missing % = the number of participants who were eligible to complete a survey the respective timepoint but did NOT complete the respective item / the number of people who were eligible to fill out a survey at the respective timepoint.

Cell percentages do not include missing and responses from participants who completed items which violated the prescribed skip pattern were omitted.

*"Other" responses and open-ended text responses will be presented in an appendix.

² Select all that apply

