initiasion center.		Pharmacist	n (%)
		Patient Services	n (%)
		Other*	n (%)
		Missing	n (%)
		Extremely Concerned	n (%)
2. How concerned are you	XX	Moderately Concerned	n (%)
from a personal safety		Somewhat concerned	n (%)
perspective about administering CABENUVA		Slightly concerned	n (%)
to PLWHIV? ³		Not concerned at all	n (%)
		Missing	n (%)
	XX	Treating HIV positive patients	n (%)
		Scheduling/Rescheduling in the correct treatment window	n (%)
3. What are your concerns		Difficulty of giving the gluteal medial injection	n (%)
about treating PLWHIV or		Ability to provide adequate privacy for patients	n (%)
administering CABENUVA? ^{1,2}		Volume of patients we may need to treat on CABENUVA	n (%)
		I have no concerns at all	n (%)
		Other*	n (%)
		Missing	n (%)
		Extremely easy	n (%)
4. CABEBUVA must be administered within a two-		Very easy	n (%)
week treatment window		Somewhat easy	n (%)
every month.	XX	Neutral	n (%)
4a. How easy or difficult do you think the appointment		Somewhat challenging	n (%)
scheduling will be? ³		Very challenging	n (%)
		Extremely challenging	n (%)

Question	Number of Participants at Baseline	Response	n (%)
		Missing	n (%)
		Extremely easy	n (%)
4. CABEBUVA must be		Very easy	n (%)
administered within a two-	XX	Somewhat easy	n (%)
week treatment window every month.		Neutral	n (%)
4b. How easy or difficult do		Somewhat difficult	n (%)
you think the appointment		Very difficult	n (%)
re-scheduling will be? ³		Extremely difficult	n (%)
		Missing	n (%)
		Phone call	n (%)
		Email	n (%)
		Fax	n (%)
5. How will you notify a	\0/	Postal Letter	n (%)
provider when a patient gets CABENUVA on time? ^{1,2}	XX	Secure electronic medical record message	n (%)
		Depends on provider preference	n (%)
		No communication necessary	n (%)
		Missing	n (%)
	XX	Phone call	n (%)
		Email	n (%)
6. How will you notify		Fax	n (%)
providers if a patient		Postal Letter	n (%)
misses a CABENUVA visit or		Secure electronic medical record message	n (%)
gets it out of window? ^{1,2}		Depends on provider preference	n (%)
		No communication necessary	n (%)
		Missing	n (%)
		Extremely easy	n (%)
	VOV.	Very easy	n (%)
7. In your opinion, how easy or difficult do you		Somewhat easy	n (%)
think the CABENUVA		Neutral	n (%)
administration will be to	XX	Somewhat difficult	n (%)
implement in your current work-flow? ³		Very difficult	n (%)
		Extremely difficult	n (%)
		Missing	n (%)
		0 – 2 patients	n (%)
8. How many CABENUVA		3 – 5 patients	n (%)

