patients do you think your infusion center can handle	XX	6 – 10 patients	n (%)
in an average week? ³		11 – 15 patients	n (%)
		16 – 25 patients	n (%)

Question	Number of Participants at Baseline	Response	n (%)
		26+ patients	n (%)
		Missing	n (%)
	XX	Extremely positive	n (%)
		Very positive	n (%)
9. Overall, what is your		Somewhat positive	n (%)
opinion about		Neutral	n (%)
administering CABENUVA for PLWHIV at your		Somewhat negative	n (%)
infusion center? ³		Very negative	n (%)
		Extremely negative	n (%)
		Missing	n (%)

¹ Select all that apply

Abbreviations: IC = infusion center; ASA = alternative site of administration; HIV = human immunodeficiency virus; PLWHIV = participants living with human immunodeficiency virus

NOTE: Missing = the number of participants who are eligible to complete a survey at the respective timepoint but did not complete respective item; Missing % = the number of participants who were eligible to complete a survey at the respective timepoint but did NOT complete the respective item / the number of people who were eligible to fill out a survey at the respective timepoint.

Cell percentages do not include missing and responses from participants who completed items which violated the prescribed skip pattern were omitted

² Within each question, response choices will be ordered by percent endorsing, descending, and ties will go in order presented to respondents. For items with more than 5 response options, the top 5 selected response options within each item at baseline will be bolded in tables for subsequent timepoints.

³ Select one response

^{*&}quot;Other" responses and open-ended text responses will be presented in an appendix

Table 1.1.2. IC/ASA Staff Roles, Attitudes, and Anticipated Procedures in Implementing CABENUVA via IC/ASAs, Month 3 (N=XX)

Question	Number of Participants at Month 3	Response	n (%)
		Extremely concerned	n (%)
		Moderately concerned	n (%)
How concerned are you from a personal safety		Somewhat concerned	n (%)
perspective about	XX	Slightly concerned	n (%)
administering CABENUVA to people with HIV? ¹		Not concerned at all (skip to 2)	n (%)
people with this:		Unsure/not applicable to role (skip to 2)	n (%)
		Missing	n (%)
		Treating HIV positive patients	n (%)
		Scheduling/Rescheduling in the correct treatment window	n (%)
1a. What are your concerns		Difficulty of giving the gluteal injection	n (%)
about treating people with HIV	VV	Ability to provide adequate privacy for patients	n (%)

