		I did not have any problems with my prior daily HIV medications	n (%)
		Missing	n (%)

Question	Number of Participants at Baseline	Response	n (%)
		Never	n (%)
7. When you were		Less than once per week	n (%)
taking daily oral HIV medication, how often		Once or twice per week	n (%)
did you not take your	XX	Three or four times per week	n (%)
HIV medicine during a typical week?1		More than five times per week	n (%)
cypioai weeki		Missing	n (%)
		Forgot	n (%)
		Social plans interfered with usual dosing time	n (%)
		Work schedule interfered with usual dosing time	n (%)
		Travel/vacation (either work or pleasure)	n (%)
8. What were your		To avoid side effects	n (%)
reasons for not taking your daily oral HIV	XX	Did not feel well	n (%)
medicine? ^{2,3}		Ran out of medication	n (%)
		Changed medication	n (%)
		I never forgot to take my daily oral meds	n (%)
	Other* Missing	Other*	n (%)
		n (%)	
		The infusion center managing my pain or soreness from CABENUVA	n (%)
		The infusion center managing the side effects from CABENUVA	n (%)
		My doctor not knowing if I have a bad reaction	n (%)
		The infusion center not aware of my other medical history	n (%)
		Infusion center not aware of my other medications and possible interactions	n (%)
		Scheduling upcoming CABENUVA visits	n (%)
		Rescheduling missed CABENUVA visits	n (%)
9.What are/were your		Forgetting my appointments for the CABENUVA visits	n (%)
biggest concerns about receiving CABENUVA at	XX	Frequency of the required visits to the infusion center clinic as well as my primary HIV doctor	n (%)
an infusion center? ^{2,3}		Transportation to the infusion center for the CABENUVA visits	n (%)
		Parking at the infusion center for CABENUVA visits	n (%)
		The infusion center hours for CABENUVA visits	n (%)
		Childcare during CABENUVA visits	n (%)
		Infusion Center not being an HIV-specific clinic	n (%)
		Others at the clinic may find out that I am HIV positive	n (%)
		Other*	n (%)
		No current worries about receiving CABENUVA at an infusion center	n (%)
		Missing	n (%)

Question	Number of Participants at Baseline	Response	n (%)
		At my HIV doctor's clinic	n (%)
		At an infusion center	n (%)
10. Where would you prefer to receive	XX	At home	n (%)
CABENUVA? ^{1,2}	^^	At a pharmacy	n (%)
		Other*	n (%)
		Missing	n (%)
11. How interested would	d you be in thes	e other ways of receiving your CABENUVA injections, if available in the fo	uture?
11a. At home,		Very interested	n (%)

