administered by a		Moderately interested	n (%)
partner as two injections in your	XX	Somewhat interested	n (%)
gluteal (buttocks) muscle (same type of		A little interested	n (%)
injections you have been/will be receiving		Not at all interested	n (%)
in this study) 1		Missing	n (%)
		Very interested	n (%)
11b. At home,		Moderately interested	n (%)
administered by a	207	Somewhat interested	n (%)
partner as two injections in your	XX	A little interested	n (%)
thigh ¹		Not at all interested	n (%)
		Missing	n (%)
		Very interested	n (%)
11- 14		Moderately interested	n (%)
11c. At home, self-administered by you as	XX	Somewhat interested	n (%)
two injections in your	ΛX	A little interested	n (%)
thigh ¹		Not at all interested	n (%)
		Missing	n (%)

¹ Select one response

Abbreviations: ART = antiretroviral therapy; HIV = human immunodeficiency virus; PLWHIV = participants living with human immunodeficiency virus.

NOTE: Missing = the number of participants who are eligible to complete a survey at the respective timepoint but did not complete respective item; Missing % = the number of participants who were eligible to complete a survey the respective timepoint but did NOT complete the respective item / the number of people who were eligible to fill out a survey at the respective timepoint.

Cell percentages do not include missing. Cell percentages do not include missing.

² Within each question, response choices will be ordered by percent endorsing descending, ties will go in order presented to respondents. For items with more than 5 response options, the top 5 selected response options within each item at baseline will be bolded in tables for subsequent timepoints.

³ Select all that apply

^{* &}quot;Other" responses and open-ended text responses will be presented in an appendix

Table 1.2.2. PLWHIV Medication Regimen: Experience, Practices, and Views, Month 3 (N=XX)

Question	Number of Participants at Month 3	Response	n (%)
1. Do you have any		Yes (go to Q2)	n (%)
concerns about continuing to receive CABENUVA at	XX	No (go to Q3)	n (%)
an infusion center? ¹		Missing	n (%)
		The infusion center managing my pain or soreness from CABENUVA	n (%)
		The infusion center managing the side effects from CABENUVA	n (%)
		My doctor not knowing if I have a bad reaction	n (%)
	XX	The infusion center not aware of my other medical history	n (%)
		Infusion center not aware of my other medications and possible interactions	n (%)
		Scheduling upcoming CABENUVA visits	n (%)

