4c. At home, self-administered by you as two injections in your thigh¹ XXX Somewhat interested n (%) A little interested n (%)			Very interested	n (%)
administered by you as two injections in your thigh¹ XXX Somewhat interested n (%) A little interested n (%)	4c. At home, self-		Moderately interested	n (%)
thigh ¹ A little interested n (%)	administered by you as	XXX	Somewhat interested	n (%)
Not at all interested n (%)			A little interested	n (%)
			Not at all interested	n (%)

			Missing	n (%)	
--	--	--	---------	-------	--

¹ Select one response

Abbreviation: HIV = human immunodeficiency virus; PLWHIV = participants living with human immunodeficiency virus NOTE: Missing = the number of participants who are eligible to complete a survey at the respective timepoint but did not complete respective item; Missing % = the number of participants who were eligible to complete a survey the respective timepoint but did NOT complete the respective item / the number of people who were eligible to fill out a survey at the respective timepoint.

Cell percentages do not include missing and responses from participants who completed items which violated the prescribed skip pattern were omitted*"Other" responses and open-ended text responses will be presented in an appendix

Table 1.2.3. PLWHIV Medication Regimen: Experience, Practices, and Views, Month 8

Table 1.3.1. PLWHIV Views on IC Administration Model, Baseline (N=XX)

Question	Number of Participants at Baseline	Response	n (%)
		Very acceptable	n (%)
		Somewhat acceptable	n (%)
		A little acceptable	n (%)
1. How acceptable is it to you to come to the	VOV.	Neutral	n (%)
infusion center for CABENUVA? ¹	XX	A little unacceptable	n (%)
		Somewhat unacceptable	n (%)
		Very unacceptable	n (%)
		Missing	n (%)
		Convenient location of the infusion center	n (%)
		Ease of parking at the infusion center	n (%)
2. What are the		Convenient hours for the infusion center	n (%)
advantages of going to the infusion center to receive CABENUVA? ^{2,3}	XX	More privacy at the infusion center	n (%)
		I like that people do not know what medication I am there to receive	n (%)
		Reduced stigma	n (%)

² Select all that apply

³ Within each question, response choices will be ordered by percent endorsing, descending, ties will go in order presented to respondents. or items with more than 5 response options, the top 5 selected response options within each item at baseline will be bolded in tables for subsequent timepoints.

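### At Month 3 the participant concern list is tabulated only among those who report a concern, while at baseline it was tabulated among everyone, and correctly skipped participants are counted as missing

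*SAP*

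**What the plan says.** **Participants, baseline** (PLWHIV SAP, Table 1.2.1 item 9). The select-all list of concerns has no gate question. Its last option is "No current worries about receiving CABENUVA at an infusion center", so a participant without concerns still answers the item. The percentage rule is "Cell percentages do not include missing".

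**Participants, Month 3** (Table 1.2.2). Item 1 asks whether the participant has any concerns about continuing at an infusion center. Yes leads to item 2 and No leads to item 3. Item 2 repeats the baseline concerns without a none option. Two notes govern the table:
- Percentages: "Cell percentages do not include missing and responses from participants who completed items which violated the prescribed skip pattern were omitted".
- Missing: "Missing = the number of participants who are eligible to complete a survey at the respective timepoint but did not complete respective item". The percentage missing is taken over everyone eligible to fill out a survey at that visit.

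A further note to the same table says that, for longer items, "the top 5 selected response options within each item at baseline will be bolded in tables for subsequent timepoints".

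**Participants, Month 8.** The SAP prints only a title: "Table 1.2.3. PLWHIV Medication Regimen: Experience, Practices, and Views, Month 8".

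**Staff** (IC/ASA Staff SAP). Baseline item 3 (Table 1.1.1) is asked of all staff and offers "I have no concerns at all". At Month 3 (Table 1.1.2), item 1 asks how concerned staff are about their personal safety. The response "Not concerned at all (skip to 2" bypasses the list in item 1a, and so does the unsure/not applicable response. The skip and Missing notes match those for participants. Footnotes 4 and 5 of that table state who was asked items 2b and 4b. Item 1a has no such footnote, and neither does participant item 2.

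**The concern.** The same list is printed at two visits on two different bases, and nothing in the table tells the reader. At baseline the base includes people without concerns. At Month 3 they are routed out by item 1, and the percentage rule keeps them out. Bolding the baseline leaders in later tables invites the reader to set the visits side by side.

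Perceptions, facilitators and barriers/concerns at Months 1, 3 and 8 form a secondary objective (Protocol Section 3; PLWHIV SAP Table A). Concerns could look more common than they are, and some comparisons with baseline could point the wrong way. A participant who said No to item 1 was eligible for the survey and did not complete item 2, so the wording places that participant in Missing. Satisfied participants would then be reported as non-response.

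**Working it through.** The plan states no figure to reproduce, so this is a check on the denominators.

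**Inputs**
- From the documents: item 9 is ungated, item 2 is asked only after Yes on item 1, and the percentage and Missing rules are as quoted.
- Assumed, because the documents do not give them: N = 100 respondents at each visit, baseline prevalence of one concern p0 = 30% (30/100), and q (the share answering Yes to item 1) ranging from 0.2 to 1.0.

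**Formulas.** Let x participants cite a given concern at Month 3.
- On the baseline basis: p3 = x/N.
- As the table would print it: x/(qN) = p3/q, so the inflation is 1/q.
- A true fall prints as a rise when p3/q > p0 and p3 < p0, that is, when q·p0 < p3 < p0.
- If everyone answers item 1 and all who are asked answer item 2, the Missing percentage for item 2 is (N − qN)/N = 1 − q.

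**One case in full.** With q = 0.4 and x = 20, the table prints 20/40 = 50.0% against 30% at baseline, an apparent rise. On the baseline basis the figure is 20/100 = 20.0%, a fall. Missing prints as 60/100 = 60%, although nobody failed to answer.

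**Range of q, with p0 = 30%**

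| q | Inflation 1/q | True p3 above which a rise prints (30% × q) | True fall to 20% prints as | True fall to 10% prints as | Missing printed |
|---|---|---|---|---|---|
| 0.2 | 5.0 | 6% | 100% (rise) | 50.0% (rise) | 80% |
| 0.4 | 2.5 | 12% | 50.0% (rise) | 25.0% (fall) | 60% |
| 0.5 | 2.0 | 15% | 40.0% (rise) | 20.0% (fall) | 50% |
| 0.6 | 1.7 | 18% | 33.3% (rise) | 16.7% (fall) | 40% |
| 0.7 | 1.4 | 21% | 28.6% (fall) | 14.3% (fall) | 30% |
| 0.8 | 1.25 | 24% | 25.0% (fall) | 12.5% (fall) | 20% |
| 1.0 | 1.0 | 30% | 20.0% (fall) | 10.0% (fall) | 0% |

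The inflation is present whenever q is below 1. The reversal appears in only some rows.

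**Staff, by comparison of the items.** The Month 3 gate concerns personal safety only, but item 1a also lists scheduling, injection difficulty, privacy and patient volume. A staff member with no safety worry may still have a scheduling concern and is never asked. The base of item 1a therefore differs from that of baseline item 3, but no recoding recovers the answers of those who skipped.

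**The case against.** The best reply is that reporting a gated follow-up among those asked is normal practice, and that the table prints what a reader needs: the Yes/No counts for item 1 sit directly above item 2, and item 2 shows n as well as a percentage. The all-respondent figure can be rebuilt. The endpoint is a descriptive summary at each visit, and change analyses are specified only for the FIM and AIM. The factor 1/q is the same for every option, so the Month 3 ranking is unaffected. The question also shifts from receiving to continuing to receive injections, so a common denominator would not make the two items identical.

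All of this is true and limits the importance of the point. It does not remove it. A reader can rebuild the figure only after noticing a change of base that no footnote declares, and the printed Missing row would remain wrong under the SAP's own definition.

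A reader might infer more than the documents support:
- **That concerns will appear to rise while falling.** This needs q·p0 < p3 < p0, and q is unknown.
- **That Month 8 has the same fault.** Participant Table 1.2.3 and staff Table 1.1.3 are titles only. PLWHIV SAP Section 2.1.3 gives the same count of 39 items for Months 3 and 8, which makes the same participant gate likely but does not show it. It says nothing about staff.
- **That the staff list can be repaired in the same way.** It cannot, because its gate asks a narrower question and has a second skip route.
- **That the whole barriers objective is compromised.** The participant disadvantages item keeps a none option at both visits, the disclosure items are ungated, and the 16-item staff concern tables are ungated with the same response categories at baseline and Month 3.

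**Conclusion.** The point holds for participant Table 1.2.2 item 2. Followed as written, the plan prints Month 3 concern percentages that are 1/q times their baseline-equivalent values, and reports designed skips as missing data. The size depends wholly on q: 5-fold at 0.2, 2-fold at 0.5, none at 1.0. A reversed trend is possible, not certain. The denominator is read from the footnotes, because the column giving the number of participants is not defined for gated items.

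Staff item 1a shares the unlabelled change of base and the Missing problem, but not the remedy. Month 8 is conditional on the same gate being used. The tables are descriptive and no primary result is touched. The change should still be made before the tables are produced, because a stated rule gives a wrong Missing figure and an undeclared change of base.

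**What to change.** **Participant item 2, Month 3** (and Month 8 if the same gate is used):
- Use all respondents to item 1 as the denominator for each concern, and count No as not citing it. This is sound because item 1 asks about any concern with continuing at an infusion center.
- Show the percentage among those asked as a labelled extra.
- Add a row for participants skipped by design, and limit Missing to those who should have answered.

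**Staff item 1a, Month 3:**
- Do not recode skipped staff as having no concerns.
- Add a footnote stating who was asked, as the table already does for items 2b and 4b.
- Show designed skips separately from Missing, and state that the item is not comparable with baseline item 3.

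The ungated disadvantages, disclosure and 16-item staff concern tables need no change of denominator.

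The cost is a few footnotes, one added row per item and a denominator change in programming. No new data are needed.
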